799 are assessed every 6 months from baseline to 5 years of therapy. Thus, analyses of bone biopsy endpoints
800 involve both within-arm and between-arm comparisons at the 3 times, while all other analyses will utilize
801 standard repeated measures methods for longitudinal data.

802 These analyses will initially include all randomized subjects who remain evaluable for the endpoints,
803 including those eligible out of the subjects currently on conventional therapy plus the 36 newly enrolled
804 subjects. However, if covariate adjustment in analyses described below indicates that there are differences
805 between these strata, then the 3 strata will be analyzed separately. The subjects who were on HPTH under
806 the previous version of the protocol will be analyzed separately using similar analysis methods,
807 recognizing the limitations of the small sample size (≤ 8). Any subject who enters menopause prior to the
808 second bone biopsy will remain in the study and will undergo the second biopsy; however, the results will
809 be reported separately and not included in the data analyses of the randomized groups. It is felt that
810 reviewing the results from a menopausal woman anecdotally may give insight into possible treatment
811 effects in a menopausal sub-population. Data will be summarized graphically and in tabular form using
812 standard descriptive statistics for categorical and continuous measures, with appropriate consideration of
813 underlying distributional assumptions. All tests of significance will be two-tailed at the 0.05 level.

814 For the bone biopsy endpoints, paired t-tests will be used to test the hypotheses that the 1, 2, and 4-year
815 changes from baseline are significantly different from zero. One-way analysis of variance (ANOVA) will
816 be used to compare these differences to each other, with protected individual linear contrasts performed if

817 the overall F-test is significant. The effects of selected baseline covariates, including gender and
818 menopausal status, will be assessed using analysis of covariance (ANCOVA) in a sensitivity analysis.
819 Exploratory graphical methods will also be used to assess distributional assumptions and potential
820 differences in responses between the strata. Log-transformation of raw data or non-parametric test
821 alternatives may be considered if indicated by these exploratory analyses.

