7.4 Analysis Methods

All study endpoints used in analyses will be summarized in tables. Continuous endpoints will be summarized over time using n, mean \pm se, median, min, max. Endpoints requiring log-transformation will also be summarized over time using geometric means with their 95% confidence limits. Ordinal endpoints will be summarized using medians, min, max, and their 10th and 90th percentiles. Categorical endpoints will be summarized using number and percent in each category.

All efficacy analyses related to the bone biopsies will be performed on the Bone Biopsy Population. All efficacy analyses other than the bone biopsy related endpoints will be performed on the Secondary Efficacy Population.

For subjects who enter menopause during the study, any of their efficacy endpoints collected during or post-menopause will be excluded from the efficacy analyses, and will have such endpoints reported separately in the subject listings.

Unless otherwise stated, all statistical inference will be based on an alpha level of 0.05 with adjustments for multiple comparisons when needed as described below. Analyses will be made using SAS (SAS Institute, Cary, North Carolina), version 9.4 or later.

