7.4.2.4 Repeated measures analyses of the non-biopsy secondary endpoints

The secondary non-biopsy secondary endpoints are listed in section 7.2.2.

Unlike the biopsy endpoints, the secondary non-biopsy secondary endpoints had measurements at baseline and then every 6 months over the 5 years of the study as compared to biopsies at baseline, 1, 2, and 4 years of hPTH treatment. As a complication, subjects were on hPTH therapy for various lengths of time due to study withdrawal and early study termination. Thus, the effects of study month are not the same for each subject with some subjects on hPTH therapy and some

subjects off hPTH therapy for the later study months. Thus, the 6-month time-points will be reduced to the following experimental time-points: baseline visit, 6-month study visit, end of hPTH therapy, and post-hPTH follow-up visit.

The effect of hPTH therapy over the experimental time-points (baseline, 6-month study visit, last hPTH treatment, and post-hPTH follow-up) on each of the non-biopsy endpoint parameters will be analyzed using repeated measures mixed models with the non-biopsy endpoint as the dependent variable, the baseline value of the non-biopsy endpoint, and study cohort as covariates, the experimental time-point as the repeated measure, and subject as the random factor. If dose is found to improve model fits in the bone-biopsy repeated measures analyses (section 7.4.2.1) then the effect of dose will be added as a covariate to these secondary repeated measures. Pairwise post hoc comparisons will be made to test for endpoints differences among the experimental time-points (baseline, 6-month study visit, last hPTH treatment, and post-hPTH follow-up). The significance of these post hoc pairwise comparisons will be corrected for multiple comparisons using Fisher's protected LSD. When the repeated measures overall effects of study time-point are not significant, Bonferroni corrections will be used to adjust the pairwise contrasts for multiplicity.

Residual analysis will be used to confirm that repeated measures model assumptions are reasonable. Log-transformations of the bone biopsy endpoints will be made if indicated by the residual analysis. The repeated measures will be fit using both a compound symmetry and an unstructured covariance structure. The better covariance structure will be selected as the model with the better Schwarz- Bayesian criterion.

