7.4.2.5 Summary of the effects of hPTH weaning on serum calcium, phosphorus, calcitriol, and biomarkers of bone turnover.

The effects of weaning subjects off hPTH will be summarized descriptively by the study PI.

Mixed models repeated measures analysis will test treatment effects on 10 outcome measures: serum calcium, serum phosphorus, 3 bone turnover markers (Osteocalcin, n-Telopeptide, and Alkaline Phosphatase), and 5 DEXA Bone Mass Density (BMD) parameters. The DEXA bone mass density measures included: AP spine BMD, femoral neck BMD, total hip BMD, Forearm BMD, and whole body BMD. Treatment effects will be summarized at three study time-points: Baseline (immediately at start of hPTH treatment), Treatment (immediately prior to Weaning, i.e. end of hPTH treatment), and Follow-up. The repeated measures analyses will be performed using each of these 10 outcome measures as the dependent variables, with random effects for subject,

and repeated fixed effects for 3 study time-points within a subject. These outcome measures will be log-transformed if necessary to normalize the data. Two covariance structures will be tested (compound symmetry and unstructured) and the covariance structure with the smallest Bayesian Information Criterion (BIC) and the best residual distributional properties will be used. Pairwise post hoc contrasts will be made to compare the effects of treatment at the study time-points. These post hoc pairwise contrasts will be corrected for multiple comparisons using Fisher's protected LSD with Bonferroni corrections when the overall effect of time is not significant.

Rho will provide figures with panel columns for the subject and the panel rows for the time course (baseline, during hPTH, through the start of weaning to the post-hPTH follow-up) of oral elemental calcium and calcitriol dosing, plasma calcium, and PTH dose.

7.4.2.6 Summary of hPTH therapy on nephrocalcinosis and nephrolithiasis by ultra sound and CT

The rate of new, stable, and progressing nephrocalcinosis and nephrolithiasis (NC/NL) in study subjects will be summarized.

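### SAP 7.4.2.4 and 7.4.2.5 choose the covariance by BIC and name no small-sample method, so unless compound symmetry holds, the time test that opens unadjusted pairwise contrasts can exceed 5%

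*SAP*

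**What the plan says.** SAP 7.4.2.4 reduces the non-biopsy visits to four time-points: "baseline visit, 6-month study visit, end of hPTH therapy, and post-hPTH follow-up visit". Each endpoint goes into a mixed model with its baseline value and study cohort as covariates, "the experimental time-point as the repeated measure, and subject as the random factor". On the covariance it says "The repeated measures will be fit using both a compound symmetry and an unstructured covariance structure", and then "The better covariance structure will be selected as the model with the better Schwarz- Bayesian criterion".

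SAP 7.4.2.5 models ten outcomes at three time-points, with no baseline covariate listed: "Two covariance structures will be tested (compound symmetry and unstructured"). There the choice rests on the smallest BIC together with the best residual behaviour.

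In both sections pairwise contrasts are "corrected for multiple comparisons using Fisher's protected LSD", with Bonferroni used only when the overall time effect is not significant. SAP 7.4 states that "all statistical inference will be based on an alpha level of 0.05", and Protocol 10.1 makes tests two-sided at that level. SAP 3 and 7.4 name SAS 9.4. Neither document names a denominator-df method or any small-sample adjustment for these models.

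**The concern.** Unstructured covariance over four visits has 10 parameters, estimated here from at most 29 subjects. A Wald F test that treats them as known rejects too often.

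Compound symmetry has two parameters, but it assumes equal variances and correlations across visits that mix off-drug states (baseline, follow-up) and on-drug states (6 months, end of therapy). The end-of-therapy visit also falls at a different treatment duration for each subject. BIC penalises the extra eight parameters heavily at this size, so it often keeps compound symmetry when it is wrong.

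The overall time test decides whether the six pairwise contrasts are each read at 0.05 or at a Bonferroni level (0.05/6 = 0.0083, if all six are counted). Inflation of that test therefore passes directly into the pairwise claims on bone markers, calcium, bone density, fatigue, walking distance and SF-36.

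**Working it through.** **Inputs**
- Nominal level 0.05: SAP 7.4 and Protocol 10.1.
- Four time-points give 3 numerator df and 6 contrasts (SAP 7.4.2.4); three give 2 numerator df (SAP 7.4.2.5).
- Cohort 3 had 19 treated subjects (SAP 9). Cohort 2 came from at most 10 (Protocol 10.3). The maximum is 19 + 10 = 29. SAP 4 repeats all efficacy analyses in Cohort 3 alone.
- Subjects per time-point are not given. N = 12, 19 and 27 are assumed. A 33% dropout (Protocol 10.2) would leave 19 × 2/3 ≈ 13 in Cohort 3.
- No df method is stated, so two are shown, both from general software knowledge: between-within (N−1) and containment with a separate random subject (3(N−1), or 2(N−1) for three levels).
- No covariance values are given, so several are assumed.

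The only stated figure is the nominal 0.05. It cannot be derived from the documents, so there is nothing to reproduce.

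**Step 1. Exact level when unstructured is fitted (complete data, no covariates)**

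With q numerator df, the Wald F is distributed under no change as (N−1)/(N−q) × F(q, N−q). Hence

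level = P[ F(q, N−q) > Fcrit × (N−q)/(N−1) ],

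where Fcrit is the 95% point of F(q, ν) and ν is the df rule.

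Example with q = 3, N = 12, containment ν = 33: Fcrit = 2.892; 2.892 × 9/11 = 2.366; P[F(3, 9) > 2.366] = 13.9%.

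| Test | df rule | N=12 | N=19 | N=27 | N=29 |
|---|---|---|---|---|---|
| Four-level | between-within | 9.2% | 7.3% | 6.5% | 6.4% |
| Four-level | containment | 13.9% | 9.9% | 8.3% | 8.0% |
| Three-level | between-within | 6.6% | 5.9% | 5.6% | 5.6% |
| Three-level | containment | 8.8% | 7.2% | 6.5% | 6.4% |

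**Step 2. The full four-level rule with BIC selection**

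This used 20,000 null trials per setting, REML, complete data and no covariates. Each cell shows between-within / containment level, with the share of trials choosing unstructured in brackets.

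| True covariance | N=12 | N=19 | N=27 |
|---|---|---|---|
| Compound symmetry, r=0.5 | 5.6 / 5.8% (4%) | 5.4 / 5.4% (1%) | 5.2 / 5.2% (0%) |
| Serial correlation 0.7 | 8.6 / 9.8% (20%) | 7.2 / 7.7% (18%) | 7.1 / 7.6% (24%) |
| SDs 1, 1.5, 1.5, 1; r=0.5 | 7.1 / 8.0% (18%) | 6.2 / 6.7% (16%) | 5.8 / 6.2% (19%) |
| SDs 1, 2, 2, 1; r=0.5 | 9.0 / 11.6% (59%) | 7.5 / 9.4% (74%) | 6.6 / 8.2% (89%) |
| SDs 1, 2, 3, 1; serial 0.6 | 9.4 / 13.8% (93%) | 7.6 / 10.2% (99%) | 6.4 / 8.3% (100%) |

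Over all nine patterns run, true compound symmetry gave 4.8-5.8%. Departures gave 5.8-9.4% (between-within) and 6.2-13.8% (containment). Compound symmetry fitted throughout gave 5.3-7.5% under those departures. With between-within df, familywise error over the six contrasts was 5.1-5.7% under compound symmetry and 6.1-8.6% otherwise; the Bonferroni branch supplied at most about 0.4 points of it.

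**Step 3. After correction**

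Unstructured fixed in advance, with the Hotelling reference that Kenward-Roger gives for complete data, ran at 4.8-5.3% in every setting. Adding the df correction but keeping BIC left 4.8-7.6%. Both changes are needed.

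**Step 4. The baseline covariate in 7.4.2.4**

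If baseline Y0 is both an outcome row and a covariate with common slope b, the baseline residual is (1−b)Y0 minus its mean. Subtracting b·Y0 from every row multiplies the determinant of the 4×4 covariance by (1−b)². With unstructured covariance and b held fixed, −2 log L (REML) therefore changes by 2(N−1)·ln|1−b|. For N = 19, moving b from 0.3 to 0.99999 changes it by 36 × [ln(0.00001) − ln(0.7)] = 36 × (−11.51 + 0.36) ≈ −402. A simulated 19-subject example fell from 8 to −393. The likelihood has no maximum, so a BIC comparison is not well defined for the model as written. Under compound symmetry the shared variance keeps it bounded.

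**The case against.** A reader might infer that the time test simply runs at 7-14%. The documents do not support that. Near compound symmetry BIC almost always keeps compound symmetry, and the level is about 5-6%. The 14% figure needs N near 12, unstructured selected and containment df together. N near 12 is an assumption about lost visits, while the calculations use complete data.

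A reader might also infer that no correction will be used. SAP 1 calls the plan abbreviated, and silence is not proof. Containment df presumes a random subject term coded on top of an unstructured matrix, which is over-parameterised. This stands as a reason to show both df rules. Between-within df still exceeds 5% when unstructured is fitted, at every N shown.

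Nor is every non-biopsy endpoint affected: SAP 7.4.2.6 only summarises nephrocalcinosis and nephrolithiasis. SAP 7.4.2.5 does not rely on BIC alone. Residual checks and log-transformation may bring variances closer together, though they need not equalise correlations.

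The simulated model omits the baseline and cohort covariates, so its rates do not describe 7.4.2.4 exactly. That is correct, but Step 4 shows that the model as written cannot be fitted sensibly with unstructured covariance at all.

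Finally, these are secondary endpoints, and the SAP makes no multiplicity correction across its eight primary ones. No confirmatory decision turns on this. The SAP nevertheless states 0.05 and uses this test as its only gate.

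**Conclusion.** The concern holds conditionally. If compound symmetry is true, the overall test is at about 5-6%. If it is not, the four-level test runs at roughly 6-10% (between-within df) or 6-14% (containment df) for an assumed N of 12 to 27. When unstructured is selected at the documents' maximum of 29, it is 6.4% or 8.0%. The three-level test of 7.4.2.5 is at about 5.6-9% when unstructured is selected; its full selection rule is not covered by these figures.

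The excess passes through the protected-LSD gate to the modelled continuous endpoints. The sizes rest on complete data, no covariates, assumed covariance patterns and df rules that the documents do not state. The degeneracy in 7.4.2.4 follows from the algebra and needs none of those assumptions. The change is worth making because a method that holds 5% is available at small cost.

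**What to change.** In SAP 7.4.2.4 and 7.4.2.5:
- Prespecify unstructured covariance with Kenward-Roger degrees of freedom (DDFM=KR).
- Remove the separate random subject term and the BIC selection.
- Name heterogeneous compound symmetry with Kenward-Roger as the fallback, used only if unstructured does not converge.

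In 7.4.2.4 also remove the baseline value as a covariate while baseline stays an outcome row; change from baseline is then read from the time contrasts. Section 7.4.2.5 lists no baseline covariate and needs no such change.

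The cost is a few lines of SAP text, one SAS option and a revised fixed-effects statement in 7.4.2.4. Intervals will be slightly wider if compound symmetry happens to be true.

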10. LIST OF PLANNED TABLES

Subject listings associated with the tables below will be provided. Experimental time refers to the baseline, last hPTH treatment, and post-hPTH follow-up visits. Additional tables (eg, those based on the results of sensitivity analysis) will be provided. Other displays, as requested by the PI may be provided as well.

Table Type	Table
Disposition	Summary of Subject Disposition
Demographics	Summary of Study Enrollment by Demographic Characteristics
hPTH Therapy	Summary of the Duration of hPTH Therapy
Primary Efficacy	Summary Statistics of Primary Bone Biopsy Endpoints by Biopsy Year. (Separate tables for Cohorts 2, 3, and Cohort 2 combined with Cohort 3)
	Repeated Measures Analysis of Primary Efficacy Analysis (Separate tables for Cohorts 2, 3, and Cohort 2 combined with Cohort 3)
Secondary Efficacy	Summary of Bone Mineralization Density Assessed by Back-Scattered Electron Imaging by Years of hPTH therapy
	Summary of Biochemical Markers of Bone Metabolism by Experimental Time Including the Statistical Significance of Changes.
	Summary of Blood and Urine Chemistries by Experimental Time Including the Statistical Significance of Changes.
	Summary of Bone Mineralization Density Assessed by DXA and Quantitative CT by Experimental Time Including the Statistical Significance of Changes.
	Summary of Nephrocalcinosis and Nephrolithiasis by Time on Study Drug
	Summary of Fatigue Symptom Inventory and 6-Minute Walk Test by Experimental Time Including the Statistical Significance of Changes.
	Summary of SF-36 Health Survey by Experimental Time Including the Statistical Significance of Changes.
Adverse Events (as provided to DSMB)	Summary of Adverse Events Occurring While on hPTH 1-34 or After Withdrawal from hPTH 1-34
	Summary of Adverse Events Occurring on or after hPTH 1-34
	Summary of Adverse Events Occurring While on Conventional Care
	Summary of Adverse Events for Subjects on Conventional Care
	Summary of Adverse Events Occurring While on hPTH 1-34 or After Withdrawal from hPTH 1-34: Current PI
	Summary of Adverse Events Occurring While on hPTH 1-34 or After Withdrawal from hPTH 1-34: Prior to Current PI
	Summary of Adverse Events Occurring While on Conventional Care: Current PI
	Summary of Adverse Events Occurring While on Conventional Care: Prior to Current PI

	Summary of Adverse Events Occurring While on hPTH 1-34 or After Withdrawal from hPTH 1-34; Related (Unlikely, Possible, Probable, or Definite) to hPTH 1-34

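### Seven to nine non-biopsy secondary outcomes have the same three contrasts tested by two different models (SAP 7.4.2.4 and 7.4.2.5), and SAP 10 does not say which model supplies the reported significance

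*SAP*

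**What the plan says.** SAP 7.4.2.4 covers all the non-biopsy secondary endpoints. Because subjects stayed on hPTH for different lengths of time, the six-monthly visits are "reduced to the following experimental time-points: baseline visit, 6-month study visit, end of hPTH therapy, and post-hPTH follow-up visit". Each endpoint gets a mixed model adjusted for its own baseline value and for cohort, with the four time-points as repeated levels and subject random. If dose improves the fit of the biopsy models, "then the effect of dose will be added as a covariate to these secondary repeated measures". Pairwise comparisons follow among the four time-points, under Fisher's protected LSD, with Bonferroni when the overall time effect is not significant.

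SAP 7.4.2.5 is headed as a summary of weaning, but it says "Mixed models repeated measures analysis will test treatment effects on 10 outcome measures". Its time-points are the start of hPTH, the end of hPTH and follow-up. It names a random subject effect and a fixed time effect, and no covariates. Pairwise contrasts follow under the same LSD and Bonferroni rule.

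SAP 7.4 puts both models in one population ("All efficacy analyses other than the bone biopsy related endpoints will be performed on the Secondary Efficacy Population") and sets one level for both ("all statistical inference will be based on an alpha level of 0.05").

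SAP 10 lists tables of bone markers, chemistries and bone density by experimental time, with the significance of changes. It then defines the term: "Experimental time refers to the baseline, last hPTH treatment, and post-hPTH follow-up visits".

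**The concern.** For each shared outcome the SAP gives two p-values for the same contrast and does not say which one is reported. The two models differ in the number of time-points, the overall gating test, the Bonferroni divisor and the covariates. An outcome near the threshold can therefore be called changed under one section and unchanged under the other, from the same data. SAP 10 does not settle it, because it takes its term from one section and its visit set from the other. The 6-month comparisons that 7.4.2.4 specifies have no place in the tables as defined. At stake is the reported significance of serum calcium, two or three turnover markers, and four or five DXA sites. SAP 1 says the document's main focus is the methods for the main publication.

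**Working it through.** **1. The plan's own count.** The ten outcomes of 7.4.2.5 are 1 (serum calcium) + 1 (serum phosphorus) + 3 (turnover markers) + 5 (DXA sites) = 10. This reproduces.

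**2. Overlap with the endpoints listed in SAP 7.2.2.3, which 7.4.2.4 analyses.**

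| 7.4.2.5 outcome | In 7.2.2.3? |
|---|---|
| Serum calcium, osteocalcin, N-telopeptide | Yes |
| AP spine, femoral neck, total hip, whole body BMD | Yes |
| Forearm BMD | Only if it is the 1/3 radius |
| Alkaline phosphatase | Only if it is the bone-specific assay |
| Serum phosphorus | No; it is tertiary (7.3.1) |

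The firm overlap is 3 + 4 = 7. Each of the two conditional matches adds one, so the range is 7 to 9.

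**3. The two models side by side.**

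| | 7.4.2.4 | 7.4.2.5 |
|---|---|---|
| Time-points k | 4 | 3 |
| Pairs k(k−1)/2 | 4×3/2 = 6 | 3×2/2 = 3 |
| Bonferroni level | 0.05/6 = 0.0083 (\|z\| 2.64) | 0.05/3 = 0.0167 (\|z\| 2.39) |
| Numerator df of overall test | 3 | 2 |
| Covariates | baseline, cohort, conditional dose | none named |

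The three pairs of 7.4.2.5 are all among the six of 7.4.2.4. The other three involve the 6-month visit.

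**4. How often the decisions differ.** The documents give no SD or correlation for these outcomes, so the following are assumptions: n = 19 (the newly enrolled treated subjects in SAP 9) and n = 25; complete data; compound symmetry with correlation 0.5 to 0.8; effects in SD units; no change at follow-up in the settings tabulated. Each simulated data set was analysed with all four visits and again without the 6-month visit:

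- Overall test: F = [n Σ(time mean − grand mean)²/(k−1)] / MSE, on (k−1) and (n−1)(k−1) df.
- Contrast: t = (end mean − baseline mean)/√(2·MSE/n).
- Significant if p < 0.05 when the overall test has p < 0.05; otherwise if p < 0.05/6 (four visits) or p < 0.05/3 (three visits).

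Results for baseline versus end of hPTH, 20,000 trials per setting:

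| True shift from baseline (SD) | n | Correlation | Significant, 4 visits | Significant, 3 visits | Opposite decisions |
|---|---|---|---|---|---|
| None | 19 | 0.5 | 2.0% | 2.6% | 1.3% |
| None | 25 | 0.8 | 1.7% | 2.4% | 1.4% |
| 6 months 0.5 only | 19 | 0.5 | 4.7% | 2.7% | 2.6% |
| 6 months 0.5 only | 25 | 0.8 | 4.9% | 2.5% | 2.6% |
| End 0.3 | 19 | 0.5 | 15.1% | 17.2% | 5.3% |
| 6 months 0.5, end 0.3 | 19 | 0.8 | 52.5% | 44.0% | 10.7% |
| 6 months 0.5, end 0.5 | 19 | 0.5 | 51.3% | 48.5% | 8.5% |
| 6 months 0.5, end 0.5 | 25 | 0.8 | 97.3% | 96.6% | 1.2% |

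Raising the 6-month shift to 0.8 SD with end at 0.3 SD gives at most 11.0% (n = 19, correlation 0.8). Disagreement is largest where power is intermediate.

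**5. What the simulation leaves out.** Baseline and cohort terms were not fitted; with complete data and compound symmetry they leave the within-subject time contrasts essentially unchanged. Dose adjustment and missing visits were not simulated and could add further differences.

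**6. Baseline as covariate and response.** In 7.4.2.4 the baseline value is also one of the repeated responses. With a covariate slope b, the baseline residual is (1−b) × baseline minus a constant. As b approaches 1, its variance approaches zero, so under the unstructured covariance the likelihood rises without bound. The 7.4.2.5 model names no such covariate.

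**The case against.** The best defence is that 7.4.2.5 serves a different purpose, the weaning period. The outcomes are secondary, no success criterion rests on them, and the two analyses will mostly agree. SAP 7.4.2.3 itself calls the secondary spectral calcium analyses more exploratory. The limited consequence and the usual agreement stand. The difference in purpose does not: 7.4.2.5 tests treatment effects including the baseline contrasts, adds five DXA sites that its heading does not mention, and is not labelled a sensitivity analysis.

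Four stronger readings are tempting and not supported.

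- A reader might infer that SAP 10 introduces a further definition of experimental time. It does not. Its three visits are those of 7.4.2.5, so there are two visit sets, and the conflict is between the term and the set.
- A reader might infer that all ten outcomes, or a definite eight, are tested twice. Phosphorus is not, and two matches depend on names the SAP does not equate.
- A reader might infer that free choice between the models inflates the false-positive rate. Counting a finding if either rule declares it gives about 3% with no change anywhere. It gives at most 5.2% when only the 6-month mean moves by 0.5 SD. Figures near 7% false positives, or 12% disagreement, arise with autoregressive data (0.7) analysed with a pooled error term. The excess false positives are covariance misfit, a separate matter.
- A reader might infer that the baseline and cohort covariates drive the disagreement. In the settings simulated, it comes from the 6-month level and the Bonferroni divisor.

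**Conclusion.** The concern holds as a conflict between stated rules: two non-identical models test the same three contrasts on seven to nine outcomes in one population, and nothing names the one that is reported. Under the assumptions above, decisions on baseline versus end of hPTH differ in about 1% of trials per outcome when nothing changes. With true changes of 0.3 to 0.5 SD they differ in about 1 to 10%, reaching 11% at the extreme. The verdicts therefore usually agree and the false-positive rate stays near or below 5%, but a borderline outcome can be reported either way. Which outcomes will be borderline cannot be told from the documents. This should be fixed; it does not threaten the primary analysis.

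**What to change.** Name one model as the only source of p-values for the shared outcomes, and take the weaning contrasts (end of hPTH versus follow-up, baseline versus follow-up) from that fit. Either model would remove the ambiguity.

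- If the four-time-point model is kept, drop the baseline value as a covariate, since baseline is already a response. Keep dose-adjusted fits apart, so that a conditional dose term cannot alter the reported contrasts.
- Keep a separate 7.4.2.5 model only for outcomes not covered elsewhere: serum phosphorus, and alkaline phosphatase if it is not the bone-specific assay. State whether it is, and whether forearm means the 1/3 radius.
- Make the SAP 10 definition of experimental time match the chosen model, including the 6-month visit if 7.4.2.4 is kept.

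The cost is a few sentences in the SAP. No new data are needed, and fewer models are run.
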